# 1.4. Clinical Summary

The safety, tolerability, and PK, along with exploratory PD of single-ascending IV doses of APD418 have been evaluated in a Phase 1 study (Study APD418-101; Part A) in heathy young adults (HYA; age 18 to 40) and healthy older adults (HOA; age 50 to 65). The potential for drug-drug interactions (DDIs), based on PK of a single IV dose of APD418 when given with a

single oral dose or after multiple oral doses of rifampin, was also evaluated in healthy adult subjects (Study APD418-101; Part B).

In Part A of the Study APD418-101, study treatment was administered as an IV infusion over 6 hours in 5 cohorts of HYA (0.17, 0.50, 1.67, 2.83, or 4.17 mg/kg/h APD418 or placebo) and 2 cohorts of HOA (0.50 or 1.67 mg/kg/h APD418 or placebo). A total of 37/39 HYA and 15/15 HOA subjects completed treatment. Of those, 30 HYA and 11 HOA subjects received APD418. Safety data for Part A of Study APD418-101 demonstrated an acceptable safety profile for both the HYA and HOA subjects. Of the HYA subjects who received APD418, a total of 15 subjects (50%) reported at least 1 treatment-emergent adverse event (TEAE); TEAEs were reported in 1 (11%) placebo treated HYA subject. The most common TEAEs were related to infusion site events, primarily infusion site pain (8 [27%] APD418 subjects; 0% placebo) and infusion site erythema (4 [13%] APD418 subjects, 0%; placebo). Other common TEAEs included upper respiratory tract infection (2 [7%] APD418 subjects; 1 [11%] placebo), infusion site swelling, infusion site warmth, arthralgia, and dizziness (each event 2 [7%] APD418 subjects; 0% placebo). In general, infusion site TEAEs were more common at higher APD418 doses (46% of subjects across 2.83 and 4.17 mg/kg/h doses), while only 12% of subjects across the range of doses (ie, 0.17, 0.50, and 1.67 mg/kg/h) planned to be studied in Study APD418-201 experienced these events (planned doses for Study APD418-201 range from 0.17 to 2.0 mg/kg/h). Two HOA subjects, 1 subject in each HOA APD418 treatment group, experienced at least 1 TEAE ( $\leq 20\%$ ); no TEAEs were reported in HOA placebo subjects. Treatment was discontinued for 2 HYA subjects (1 subject each in 0.50 and 4.17 mg/kg/h cohorts), who experienced Grade 2 TEAEs at the infusion site, which were considered not related to study drug by the Investigator. No serious adverse events (SAEs) or deaths were reported. There were no clinically significant or concerning findings in vital signs, electrocardiogram (ECG), clinical laboratory (including high-sensitivity cardiac troponin T [hs-cTnT]), and echocardiogram (ECHO) data sets, and overall no clinically identified risks for APD418 in this study.

PK data from Study APD418-101 in healthy human volunteers showed that APD418 plasma concentrations generally increased rapidly during the IV infusion. Visual assessment of plasma concentrations suggested that plasma concentrations close to steady state occurred prior to end of infusion, at which point APD418 demonstrated a rapid decrease in plasma concentrations. Mean residence time (MRT) was  $\leq$  4 hours and reflects a relatively short residence time of APD418 in the body. Consistent with the short MRT, the area under the concentration-time curve from time 0 to 24 hours (AUC0-24) comprised > 95% of the AUC0-∞ and suggests clearance of most drug from the body by 24 hours postdose. Mean exposure to APD418 increased proportionately with dose. APD418 PK in HOA subjects was similar to HYA subjects at the 3 mg/kg dose level. The 10 mg/kg dose administered to HOA subjects resulted in a small increase (approximately 1.2-fold) in exposure to APD418 in HOA compared to the HYA subjects. APD418 exposures achieved in healthy human volunteers spanned and exceeded the range of pharmacologically active concentrations in the dog model of HF; no clinically identified risks were observed across this exposure range. Renal clearance comprised approximately 15% of total clearance in both HYA subjects and HOA subjects.

# 1.5. Benefit-Risk Considerations

Nonclinical findings suggest that in the setting of HFrEF, APD418 improves cardiac performance, which in the target population of patients with decompensated HFrEF may lead to faster hemodynamic stabilization. An improved clinical course of recovery is expected to be associated with reduced in-hospital WHF events, including in-hospital death and length of hospitalization, and potentially improvement in clinical outcomes.

In this Phase 2, proof-of-mechanism study, hemodynamic effects will be investigated in stable advanced chronic HFrEF patients (LVEF  $\leq 35\%$  for at least 4 months, New York Heart Association [NYHA] Class II-IV). It is anticipated that the population chosen for this study will exhibit elevated expression of  $\beta$ 3-AdrR owing to their disease status and medical history (documented history of HFrEF; ie, LVEF  $\leq 35\%$  for at least 4 months) and as such could benefit from APD418-mediated improvement in CO. Thus, this population presents a suitable setting for the first-in-patient assessment of the safety, tolerability, and hemodynamic effects of APD418.

As of the date of this protocol, there are no clinically identified risks for APD418. Safety data for Part A of Study APD418-101, in which APD418 was administered as an IV infusion over 6 hours, demonstrated an acceptable safety profile for both the HYA and HOA subjects.

Extended single-dose, GLP-compliant, toxicity studies of APD418 administered as a 6-hour IV infusion were conducted in rats and dogs to assess acute and delayed toxicity, reversibility, and TK. These studies identified the following potential targets of APD418 toxicity: CNS, kidney, liver, and infusion site that demonstrated reversibility and are monitorable in the planned clinical study. Human safety data collected to date in Study APD418-101 have not identified any safety risks (including those observed in nonclinical studies) up to the highest dose administered. Corresponding exposures were approximately 1.8- ( $C_{max}$ ) to 2.3-fold (AUC0- $\infty$ ) higher than observed in the dog at the NOAEL.

The safety monitoring practices employed by this protocol (ie, physical examination, vital signs, safety 12-lead ECG, clinical laboratory tests including hs-cTnT, concomitant medications, and AE monitoring) are adequate to monitor and assess subject safety.

The risks of participation are primarily those associated with adverse reactions to the study treatment, although there may also be some discomfort from collection of blood samples and other study procedures.

Further description of identified risks, any potential risks, and the reference safety information for APD418 are provided in the current edition of the IB.

# 2. **OBJECTIVES**

## Primary Objective

• To assess the effect of IV infusion of APD418 on hemodynamic status based on cardiac index (CI) in subjects with HrEF

## Secondary Objectives

- To assess the effect of IV infusion of APD418 on additional hemodynamic, vital sign, and systolic function parameters in subjects with HFrEF
- To assess the PK of IV infusion of APD418 in subjects with HFrEF
- To assess the safety and tolerability of IV infusion of APD418 in subjects with HFrEF

## Exploratory Objectives

- To assess select exposure-response (PK/pharmacodynamic [PD]) relationships in subjects with HFrEF
- To assess the relationships between select subject/disease characteristics and select PD measures in subjects with HFrEF
- To assess the effect of IV infusion of APD418 on markers of renal function in subjects with HFrEF
- To assess the effect of IV infusion of APD418 on cardiac biomarkers in subjects with HFrEF
- To assess the effect of IV infusion of APD418 on additional systolic and diastolic function parameters in subjects with HFrEF
- To assess the effect of IV infusion of APD418 on urine output in subjects with HFrEF
- To assess the effect of IV infusion of APD418 on body weight in subjects with HFrEF
- To assess the OATP genotype

# **3. STUDY DESIGN**

[figure not shown]
# **3.1. Overall Design**

This is a Phase 2, multicenter, randomized, double-blind, placebo-controlled, single-dose study assessing the hemodynamic effects, safety, tolerability, and PK of APD418 in subjects with HFrEF to be conducted in 2 parts (Part A and Part B). Each part consists of a Screening Period (up to 21 days in Part A and up to 14 days in Part B), a single dose of randomized study treatment (APD418 or placebo) as a 6-hour IV infusion on Day 1 (Dosing Period) followed by an 18- to 24-hour in-clinic observation period (Postdose Period), and a Follow-Up phone call 7 days (± 2 days) after discharge (Figure 1). Subjects participating in Part A cannot participate in Part B.

On Day 1, potential eligible subjects (per initial Screening criteria) will undergo additional eligibility assessments during the Predose Period on Day 1. Hemodynamic eligibility criteria based on right heart catheterization (RHC) will be assessed at Baseline for final confirmation of eligibility and randomization. Hemodynamic parameters based on RHC will be assessed at the end of Baseline (after at least 2-hour stabilization period), during the Dosing Period throughout the study treatment administration (6-hour IV infusion), and for an additional 1 hour after cessation of study treatment administration. Subjects will continue to be observed during the Postdose Period for a minimum of 18 hours after the end of study treatment administration for PD, PK, and safety assessments prior to discharge on Day 2. Subjects will be contacted by phone call for follow-up 7 days ( $\pm 2$  days) after discharge.

This study has an adaptive design, in which dose escalation in Part A will inform dose expansion in Part B. Part A is a single-ascending dose (SAD) study planned to consist of 5 cohorts. In each cohort, subjects will be randomized to APD418:placebo in a 5:2 ratio. Randomization will be stratified by Screening LVEF (> 25%,  $\leq 25\%$ ). Following completion of all planned cohorts in Part A, 2 APD418 doses studied in Part A will be selected for expansion in Part B. Part B is a parallel-treatment group study planned to consist of a placebo group and 2 APD418 treatment groups by randomizing additional subjects in 1:1:1 ratio (15 subjects are planned in the placebo group and each APD418 treatment group; Figure 1). Randomization will be stratified by Screening LVEF (> 25%,  $\leq 25\%$ ) and baseline carvedilol use (yes, no).

Each subject will receive a single dose of study treatment as an IV infusion over a duration of 6 hours. The initial APD418 dose to be studied in the first cohort of Part A will be 0.17 mg/kg/h (total dose 1 mg/kg). After 7 subjects have completed treatment in each cohort in Part A, an assessment of the safety/tolerability and PK data will be conducted by the dose escalation committee (blinded data review by the Sponsor and Investigator representatives) to determine whether dose escalation to the next dose level in Part A can occur. Doses for each subsequent cohort in Part A may be adjusted depending on the safety, tolerability, and PK results of previous cohort(s). The maximum dose in the study will not exceed 2 mg/kg/h (12 mg/kg) without a protocol amendment. At the conclusion of Part A, the dose selection committee will perform safety/tolerability and PD data assessment to identify 2 APD418 doses to be expanded in Part B (unblinded review of Part A data by the Sponsor representatives who are not directly involved in study conduct; site staff, and sponsor representatives involved in study conduct will remain blinded throughout the study). Additional details about the dose escalation and the dose selection process are described in Sections 10.6.2 and 11.9. Additional subjects and/or cohorts may be enrolled in the study as described in Sections 6.4 and 11.9. The sample size will not increase by more than approximately 15% without a protocol amendment.

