## Number of subjects (planned):

Approximately 80 subjects (25 placebo; 55 APD418) are planned to be enrolled in the study. In Part A, 5 cohorts are planned and 7 subjects are planned to be enrolled in each cohort (5 APD418:2 placebo per cohort; total N = 35). In Part B, 2 APD418 doses assessed in Part A will be expanded by enrolling 45 additional subjects (15 subjects are planned in the placebo group and each APD418 treatment group; total N = 45).

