# 6.4. Method of Assigning Subjects to Treatment

Each subject will be assigned a unique identification number upon Screening. Eligible subjects will be centrally randomized into the study using an interactive response technology (IRT) system. In Part A, subjects who complete the study Screening assessments and meet all the eligibility criteria will be randomized to study treatment in a 5:2 ratio (APD418:placebo), stratified by Screening LVEF (> 25%,  $\leq 25\%$ ). In Part B, subjects who complete the study Screening assessments and meet all the eligibility criteria will be randomized to study treatment in a 1:1:1 ratio (2 doses of APD418:placebo), stratified by Screening LVEF (> 25%,  $\leq 25\%$ ) and baseline carvedilol use (yes, no).

Subject identification numbers will be 12 characters in length, including dashes, 201-CCSS-XXX. The first 3 digits represent the study number, the 4 digits following the first dash represent the combination of country code (CC) and the site number (SS), and the last 3 digits represent the subject number (XXX). Subject numbers will be assigned strictly sequentially at every site as subjects become eligible for enrollment, starting from 001. If a subject withdraws their participation in the study, then their unique subject number cannot be reused.

After the initial 7 subjects in each cohort in Part A have been randomized, subsequent subjects may be screened and, if possible, will not be randomized until the next dose level has been set; however, if it is not possible for the subject to wait for randomization into the subsequent dose cohort, the subject may be enrolled in the current dose cohort.

In Part A, in the event that a subject does not complete at least 4 hours of infusion and scheduled RHC assessments in that period, an additional subject may be allocated within the cohort to the same treatment as the discontinued subject at the discretion of the Sponsor. Additional subject(s) will only be enrolled in cases in which discontinuation was not the result of an AE considered probably related or related to study drug in the opinion of the Investigator, including the following:

- Technical issues resulting in incomplete study treatment administration
- Withdrawal based on subject or Investigator decision (not associated with an AE considered probably related or related to study drug in the opinion of the Investigator)

The sample size will not increase by more than approximately 15% without a protocol amendment.

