## **10.6.2.** Dose Escalation Stopping Criteria

Safety data will be monitored in a blinded manner on an ongoing basis throughout the duration of the study. After treatment of each cohort in Part A, an assessment of the safety/tolerability and PK data will be conducted by the dose escalation committee (blinded data review by the Sponsor and Investigator representatives) to determine whether dose escalation to the next dose level in Part A can occur. Doses for each subsequent cohort in Part A may be adjusted depending on the safety, tolerability, and PK results of previous cohort(s).

The dose escalation committee will use the following safety-related criteria per cohort to preclude escalation to the next planned dose level in Part A:

- Two or more subjects experience an SAE considered probably related or related to study drug in the opinion of the Investigator and the dose selection committee
- Two or more subjects experience an AE Grade 3 or higher related to clinical instability associated with hemodynamic/arrhythmia events requiring intervention (pharmacologic or mechanical) considered probably related or related to study drug in the opinion of the Investigator
- Two or more subjects experience a CNS-associated AE Grade 3 or higher considered probably related or related to study drug in the opinion of the Investigator
- Three or more subjects experience an infusion site related AE Grade 3 or higher considered probably related or related to study drug in the opinion of the Investigator
- Two or more subjects experience a clinically significant increase in ALT or AST, and TBIL, indicative of drug-induced liver injury. For subjects with values < 2× ULN prior to dosing, this criterion is met with ALT or AST ≥ 3 × ULN, and TBIL ≥ 2 × ULN, following study treatment administration. For subjects with values ≥ 2 × ULN prior to dosing, a 100% increase from baseline values meets the criterion

- Two or more subjects experience clinical worsening of renal function requiring intervention (pharmacologic or mechanical; eg, intensification of diuretic treatment due to renal function deterioration or the need for dialysis)
- Mean cohort  $C_{max}$  exceeds 5700 ng/mL and/or  $AUC_{0\mathchar`-\infty}$  with the 6-hour infusion exceeds 39,000 ng  $\cdot$  h/mL

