# **11.2.** Determination of Sample Size

Approximately 80 subjects are planned to be enrolled in this study (35 in Part A and 45 in Part B). It is assumed that CI, as measured with RHC, from Baseline to end of infusion is normally distributed with a mean of 2.0 and SD of 0.5. Sixty-five evaluable subjects (20 subjects in each of the 2 APD418 treatment groups and 25 in placebo) is sufficient to achieve at least 80% power to detect a treatment effect of 0.45 in favor of APD418 (a clinically significant improvement of 22.5% from placebo) between each of the APD418 treatment groups and placebo by a 2-sample t-test using a 2-sided significance level of 0.05.

The primary endpoint analysis will be based on pooled data from subjects in Part A and Part B. There will be 2 APD418 treatment groups of 20 subjects each (planned to consist of 5 subjects from Part A and 15 subjects from Part B) and one placebo treatment group of 25 subjects (planned to consist of 10 subjects from Part A and 15 subjects from Part B).

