# 11.3. Stratification

In Part A, randomization will be stratified by Screening LVEF (> 25%,  $\leq$  25%). In Part B, randomization will be stratified by Screening LVEF (> 25%,  $\leq$  25%) and baseline carvedilol use (yes, no).

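### Does stratifying seven-subject Part A cohorts by LVEF undo the 5:2 split that escalation and the primary analysis rely on?

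*Combined protocol and SAP*

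**What the plan says.** The synopsis, under the planned number of subjects, sets the cohort size and split: "7 subjects are planned to be enrolled in each cohort (5 APD418:2 placebo per cohort; total N = 35". Section 3.1 applies the ratio inside each cohort and adds stratification in the next sentence: "In each cohort, subjects will be randomized to APD418:placebo in a 5:2 ratio. Randomization will be stratified by Screening LVEF". Section 11.3 repeats the factor: "In Part A, randomization will be stratified by Screening LVEF", with the cut at 25%.

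On mechanism, Section 6.4 says only this: "Eligible subjects will be centrally randomized into the study using an interactive response technology (IRT) system". It gives no block size, does not say whether blocks restart with each cohort or run on, and states no cohort-level limit. It does allow a cohort to exceed seven when a subject cannot wait for the next dose level, and it allows some discontinued subjects to be replaced in the same arm.

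Two parts of the plan use the split. Escalation is reviewed "After 7 subjects have completed treatment in each cohort in Part A", by a committee that is blinded, against fixed counts in Section 10.6.2 such as "Two or more subjects experience an SAE considered probably related or related to study drug". Section 11.2 builds each selected dose group of 20 as "planned to consist of 5 subjects from Part A and 15 subjects from Part B", and the placebo group of 25 as 10 from Part A and 15 from Part B.

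**The concern.** A permuted block that gives 5:2 exactly must hold seven subjects or a multiple of seven. A cohort is exactly seven. If those seven divide between two LVEF strata, each with its own list, neither list reaches the end of a block, and the cohort's placebo count becomes random, anywhere from none to four.

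Two things would then be at stake. The escalation thresholds are fixed counts, so a cohort with three or four active subjects would be judged by the same limits as one with five, and a blinded committee would not routinely see the shortfall. The group sizes behind the power statement also assume five active subjects per selected dose and ten placebo from Part A. On this view stratification buys little in return, because two placebo subjects per cohort cannot be balanced over two strata in any useful way.

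**Working it through.** **Inputs from the plan.** Seven per cohort at 5:2 and five cohorts (synopsis, Section 3.1); two LVEF strata (Section 11.3); groups of 20, 20 and 25, effect 0.45, SD 0.5, two-sided 0.05 (Section 11.2); stopping count of two (Section 10.6.2).

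**Assumptions, not in the plan.** A fresh permuted block of seven (five active, two placebo) in each stratum of each cohort; a stratum share between 5% and 50%; illustrative event rates of 10%, 20% and 30% per active subject.

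**1. The plan's own figures.** 5 × 7 = 35; 5 × 2 + 15 = 25 placebo; 5 + 15 = 20 per dose. The noncentrality is 0.45 / (0.5 × √(1/20 + 1/25)) = 0.45 / (0.5 × 0.3) = 3.0 on 43 degrees of freedom. Power is 83.5% by the t-test (85.1% by the normal approximation), so the stated 80% holds.

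**2. Cohort split, given how the seven divide.** The placebo count among the first n of a block is hypergeometric (2 in 7), and the cohort count is the sum over the two strata. For a 4/3 division, the stratum of four has 0, 1 or 2 placebo with probability 1/7, 4/7, 2/7, and the stratum of three with 2/7, 4/7, 1/7. Then P(exactly 2) = 1/49 + 16/49 + 4/49 = 21/49 = 42.9%, a miss rate of 57.1%. The miss rate is 54.4% at 5/2, 40.8% at 6/1 and 0% at 7/0.

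**3. Averaged over divisions** (binomial in the stratum share):

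| Share in one stratum | Cohorts not exactly 5:2 |
|---|---|
| 5% | 12.9% |
| 10% | 23.4% |
| 20% | 38.4% |
| 30% | 47.4% |
| 40% | 52.1% |
| 50% | 53.6% |

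If blocks run on across cohorts, the miss rate is about 43%, 55% and 58% at shares of 10%, 30% and 50%. If the randomization system caps each cohort at five and two, it is 0%.

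**4. Direction and size of the misses.** At a 50% share, placebo counts of 0, 1, 2, 3, 4 have probability 2.98%, 23.81%, 46.43%, 23.81%, 2.98%. Within one subject of plan: 23.81 + 46.43 + 23.81 = 94.05%. Fewer than five active: 23.81 + 2.98 = 26.8% (23.7% at a 30% share). As many cohorts gain active subjects as lose them.

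**5. Escalation count.** P(two or more of n active subjects have an event) at a 30% rate is 21.6%, 34.8%, 47.2%, 58.0% and 67.1% for n = 3 to 7. Weighted by step 4: 0.0298 × (0.2160 + 0.6706) + 0.2381 × (0.3483 + 0.5798) + 0.4643 × 0.4718 = 0.0264 + 0.2210 + 0.2190 = 46.6%, against 47.2% with exactly five. The same sum gives 8.3% against 8.1% at a 10% rate, and 26.3% against 26.3% at 20%.

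**6. Primary analysis.** At a 50% share with fresh blocks, the Part A placebo total has mean 10, SD 1.9 and 95% range 6 to 14. With blocks that run on across cohorts the range is 9 to 11. Averaging the power in step 1 over the fresh-block distribution, with 15 per group from Part B, gives 83.3%, and the chance that power falls below 80% is about 0.4%.

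**The case for a change.** The strongest case for a change is that the plan promises a split per cohort, specifies a procedure that under either conventional block set-up often misses it, and then bases blinded decisions on fixed counts. An average does not help the particular cohort that is short. With three active subjects the chance of reaching the threshold at a 30% rate is 21.6% rather than 47.2%. The cohort mean of Cmax or AUC, also a stopping criterion, would be less precise if taken over active subjects: √(5/4) gives a standard error about 12% larger with four, and √(5/3) about 29% larger with three. One unstratified block of seven would be cheap, and LVEF could stay in the model.

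Some of this stands. The documents do not say how five and two are kept, and a committee on blinded data would not routinely see a departure. The rest carries less weight. The three-active case arises in about 3% of cohorts even at the least favourable share. Section 10.6.2 does not tie its counts to five exposed subjects, has the committee weigh overall safety and PK as well, and allows an unblinded look by the dose selection committee if warranted.

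The remedy also has a price. Blocks that run on across cohorts within LVEF stratum hold the Part A placebo total close to ten and keep the active-to-placebo ratio steady within each stratum of the pooled data, which an unstratified block does not do for LVEF. The MMRM is written in terms of the randomization stratification factors, so dropping one in Part A would mean rewording the model. And a single block of seven does not fix the ratio in a cohort that grows past seven, which Section 6.4 permits; the biostatistics note to file records 15 subjects in Cohort 2.

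**Conclusion.** No change to the plan is needed. This is an unstated randomization detail that whoever specifies the randomization system can settle with a cohort cap, together with a fair trade-off between exact cohort counts and LVEF balance in the pooled data. It is not shown that stratification undoes the 5:2 split: the miss rate is 0% with a cap and 13% to 54% under fresh stratified blocks of seven, a block design and range of stratum shares that are assumptions.

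Even at the least favourable share of 50%, the average effect is small: about half a percentage point or less on the chance of two or more active subjects with an event at rates of 10% to 30%, and 0.2 points of power, which stays above the stated 80%. The counts are given as planned figures, and expected counts do not move. Dropping stratification in Part A would exchange one modest imperfection for another. Writing the cohort rule into Section 6.4 would record a missing detail without altering the design or any conclusion drawn from it.
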